5.2.3 Exploratory objectives for Part B

Exploratory objective 1:

To further characterize antibody responses (eg, IgA/IgG subclass binding, epitope mapping, Ab avidity, infected cell binding, linear peptide array)

Exploratory objective 2:

To characterize Fc-mediated antibody functions (eg, fragment crystallizable receptor [FcR] array, antibody-dependent cellular phagocytosis [ADCP], antibody-dependent neutrophil phagocytosis [ADNP], antibody-dependent cellular cytotoxicity [ADCC], and/or complement binding/deposition)

Exploratory objective 3:

To further characterize neutralizing antibody responses using diagnostic mutants of HIV-1 Env pseudotyped viruses in the TZM-bl assay

Exploratory objective 4:

To analyze the B cell repertoire including somatic hypermutation, affinity maturation, CDRH3 length, and other signatures of bnAb class epitopes

Exploratory objective 5:

To apply systems biology approaches (eg, RNAseq, LC-MS) to examine transcriptomic, and metabolomic and/or proteomic profiles of innate and adaptive immune responses

Exploratory objective 6:

To characterize Env-specific B and CD4+ T cells (including Tfh/pTfh) and antigen receptor sequences using samples such as PBMC, lymph node fine needle aspirates, bone marrow aspirates, or leukapheresis

Exploratory objective 7:

To assess polyclonal serum Ab (Fab) binding to Env epitopes using electron microscopic imaging

Exploratory objective 8:

To measure Env-specific antibody levels in mucosal secretions and tissues using a quantitative immunoassay and/or immunohistochemistry (IHC)

Exploratory objective 9:

To identify the regions and epitopes of the BG505 SOSIP.664 gp140 protein targeted by CD4+ T cells in response to vaccination

Exploratory objective 10:

To further evaluate immunogenicity of each vaccine regimen, additional immunogenicity assays may be performed in a subset of participants, including on samples from other timepoints, based on the HVTN Laboratory Assay Algorithm

Exploratory objective 11:

To conduct analyses related to furthering the understanding of HIV, immunology, vaccines, adjuvant effects, and clinical trial conduct

5.3 Objectives and endpoints for Part C

5.3.1 Primary objectives and endpoints for Part C

Primary objective 1:

To evaluate the safety and tolerability of IM administration of Trimer 4571 (BG505 SOSIP.664 DS gp140) with 3M-052-AF + Alum.

Primary endpoint 1:

Signs and symptoms of local and systemic reactogenicity and laboratory measures of safety, AEs, expedited AEs, and AESIs.

Primary objective 2:

To evaluate the neutralizing antibody response induced by Trimer 4571 (BG505 SOSIP.664 DS gp140) with 3M-052-AF + Alum.

Primary endpoint 2:

Response rate and magnitude of serum antibody neutralization of autologous (HIV-1 BG505) and other heterologous tier-2 HIV-1 strains, as measured by TZM-bl assay 2 weeks after the second and third vaccinations.

5.3.2 Secondary objectives and endpoints for Part C

Secondary objective 1:

To test whether a 3-mcg dose of 3M-052-AF + Alum is sufficient to generate autologous serum antibody neutralization (HIV-1 BG505) and other heterologous tier-2 HIV-1 strains, as measured by TZM-bl assay 2 weeks after the second and third vaccinations.

Secondary endpoint 1:

Response rate and magnitude of serum antibody neutralization of autologous (HIV-1 BG505) and other heterologous tier-2 HIV-1 strains, as measured by TZM-bl assay 2 weeks after the second and third vaccinations, comparing the 5-mcg dose of the 3M-052-AF + Alum with the 3-mcg dose of 3M-052-AF + Alum.

Secondary objective 2:

To evaluate and compare the peak and durability of serum binding antibody responses elicited by BG505 SOSIP.664 gp140 adjuvanted with 3 mcg of 3M-052-AF+Alum, and by Trimer 4571 adjuvanted with 5 mcg of 3M-052-AF+Alum with Part B groups

Secondary endpoints 2:

Response rate, magnitude, and breadth of IgG binding antibody responses to HIV BG505 SOSIP.664 gp140, Trimer 4571, and HIV-1 gp120 and gp140 variant strains (to determine off-target non-neutralizing Abs) as measured by BAMA 2 weeks after the second vaccination and 2 weeks, 6 months, and 12 months after the third vaccination

Secondary objective 3:

To evaluate and compare the peak and durability of BG505 SOSIP.664 gp140-specific B cells elicited by BG505 SOSIP.664 gp140 adjuvanted with 3 mcg of 3M-052-AF+Alum, and by Trimer 4571 adjuvanted with 5 mcg of 3M-052-AF+Alum with Part B groups

Secondary endpoint 3:

Response rate and magnitude of memory IgG+ B cells binding to BG505 SOSIP.664 gp140 tetramers as measured by multiparameter flow cytometry 2 weeks after the second vaccination and 2 weeks, 6 months, and 12 months after the third vaccination

Response rate and magnitude of BG505 SOSIP.664 gp140 antigen-specific plasmablasts as measured by multiparameter flow cytometry 1 week after the second and third vaccinations

Secondary objective 4:

To evaluate Env-specific CD4+ T-helper subpopulations, phenotypes and functions elicited by BG505 SOSIP.664 gp140 adjuvanted with 3 mcg of 3M-052-AF+Alum, and by Trimer 4571 adjuvanted with 5 mcg of 3M-052-AF+Alum

Secondary endpoint 4:

Percent HIV Env-specific cytokine-expressing CD4+ T cells in blood by intracellular cytokine staining (ICS) multiparameter flow cytometry and polyfunctional subset analysis 2 weeks after the second vaccination and 2 weeks, 6 months, and 12 months after the third vaccination

Secondary objective 5:

To evaluate innate immune responses and baseline predictors, compare the innate immune responses elicited by BG505 SOSIP.664 gp140 adjuvanted with 3 mcg of 3M-052-AF+Alum, and by Trimer 4571 adjuvanted with 5 mcg of 3M-052-AF+Alum after the first vaccination, and correlate with adaptive immune responses

Secondary endpoints 5:

Alterations in blood leukocyte populations during the innate response (day 1, 3 and 7) relative to prevaccine levels (day 0)

Alterations in RNAseq expression of leukocyte and/or immune cells (lymphocyte populations, natural killer (NK) cells, dendritic cell (DC) subsets, monocytes subsets, and granulocytes) (days 1, 3, and 7) relative to prevaccine levels (day 0)

Alterations of concentrations of immune cytokines and chemokines in serum samples postvaccination (days 1, 3, 7) relative to prevaccine levels (day 0)

Secondary objective 6:

To characterize systemic inflammatory markers among participants with moderate to severe reactogenicity after any vaccination

Secondary endpoint 6

Blood cell subpopulation dynamics by multiparameter flow cytometry, gene expression alterations by RNAseq/transcripts and soluble cytokine/inflammatory mediator alterations comparing day of last vaccination and day of visit for moderate to severe reactogenicity

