the slowest processes in the history of medicine" (59). This highlights the need to develop standardized predictive models to assess safety, including adverse events (AE), pre-existing genetic variations in innate immunity and the application of systems approaches to define early biomarkers of adjuvant activity and safety signals, such as genomics, transcriptomics, proteomics and metabolomics. This study offers a unique opportunity to systematically assess the safety of multiple adjuvants with one vaccine antigen and contribute a potential expanded safety marker panel. While discordant adjuvant effects may be seen when formulated with different antigens, a safety marker panel that can be used in future studies of novel HIV and non-HIV vaccine adjuvants could be beneficial in preventing infections of major public health importance.

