To evaluate innate immune responses and baseline predictors, compare the innate immune responses elicited by BG505 SOSIP.664 gp140 with various adjuvants (CpG 1018 + Alum, 3M-052-AF + Alum, GLA-LSQ, or Alum) after the first vaccination, and correlate with adaptive immune responses

Secondary endpoints 5:

Alterations in blood leukocyte populations during the innate response (day 1, 3 and 7) relative to prevaccine levels (day 0)

Alterations in RNAseq expression of leukocyte and/or immune cells (lymphocyte populations, natural killer (NK) cells, dendritic cell (DC) subsets, monocytes subsets, and granulocytes) (days 1, 3, and 7) relative to prevaccine levels (day 0)

Alterations of concentrations of immune cytokines and chemokines in serum samples postvaccination (days 1, 3, 7) relative to prevaccine levels (day 0)

Secondary objective 6:

To characterize systemic inflammatory markers among participants with moderate to severe reactogenicity after any vaccination

Secondary endpoint 6

Blood cell subpopulation dynamics by multiparameter flow cytometry, gene expression alterations by RNAseq/transcripts and soluble cytokine/inflammatory mediator alterations comparing day of last vaccination and day of visit for moderate to severe reactogenicity

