9.10 Assessments of reactogenicity

For all participants, baseline assessments are performed before and reactogenicity assessments are performed after each vaccination. All reactogenicity symptoms are followed until resolution and graded according to the Division of AIDS Table

for Grading the Severity of Adult and Pediatric Adverse Events, Corrected Version 2.1, July 2017, except as noted in Section 11.2.2.

The reactogenicity assessment period is 7 full days for Part A and Part B and 14 full days for Part C following each vaccination per the assessment schedule shown in Table 9-1. Participants are instructed to record symptoms using a Participant Diary. Contacts between the participant and the site staff should take place at least once between 1-3 days postvaccination. In general, a participant who self-reports any postvaccination reaction greater than mild is seen by a clinician within 48 hours after onset, unless the reaction is improving and/or has completely resolved. Clinic staff will follow new or unresolved reactogenicity symptoms present at day 7 (Parts A & B) or day 14 (Part C) to resolution.

Reactogenicity events are reported using CRFs that correspond to the time of assessment in Table 9-1. Reactogenicity assessments include assessments of systemic and local symptoms, and vaccine-related lesions. Events not listed on a CRF, or with an onset after the reactogenicity assessment period (day of vaccination and 7 full days after for Part A and Part B and 14 full days after for Part C), or those meeting SAE/adverse events requiring expedited reporting according to DAIDS criteria, are recorded on an adverse event log form.

Table 9-1 Schedule of reactogenicity assessments

Day	Time	Performed by
0 ^a	Baseline: before vaccination	HVTN CRS clinician
	Early: 25-60 minutes after vaccination	HVTN CRS clinician
	Between early assessment and 11:59pm day 0	HVTN CRS clinician or participant
1-7 ^b	Between 12:00am and 11:59pm on the respective day	HVTN CRS clinician or participant
1-14 ^c	Between 12:00am and 11:59pm on the respective day	HVTN CRS clinician or participant

^a Day of vaccination

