9.10.1 Assessment of systemic and local symptoms

Systemic symptoms include increased body temperature, malaise and/or fatigue, myalgia, headache, chills, arthralgia, and nausea. Local symptoms include pain and/or tenderness at the injection site. The daily maximum severity reached for each symptom during the assessment period is reported.

Body temperature is measured by oral or infrared thermometry. All temperatures must be measured by non-axillary thermometry. This includes temperatures taken in the clinic, as well as temperatures taken by participants during the reactogenicity period.

^b New or unresolved reactogenicity symptoms present on day 7 are followed until resolution for Parts A and B

^c New or unresolved reactogenicity symptoms present on day 14 are followed until resolution for Part C

Temperature is reported in degrees Celsius. If temperature is measured in Fahrenheit, the conversion to Celsius should be documented in the participant's chart note. A measurement is taken once daily during the assessment period and should be repeated if participant is feeling feverish.

Participants with evidence of moderate to severe reactogenicity may be asked to come to the clinic for additional assessment and/or blood sampling.

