Innate immunity and inflammation assays	 	··········					A				***************************************	200000000000000000000000000000000000000						***************************************	8		
Phenotyping	CSR	HVTN Labs	ACD	8.5mL	_	8.5	8.5	8.5	8.5	_	8.5	_	_		8.5	T —	T -		_	I –	51
RNA gene expression	CSR	HVTN Labs	Tempus	3mL	_	3	3	3	3	_	3	_	3		3		3		_	_	24
Serum cytokines/chemokines	CSR	HVTN Labs	SST	5mL	_	5	5	5	5	_	5	_	_		5	T	T —		_	l –	30
STORAGE			 	 	O		····			0		***************************************		***************************************	***************************************		***************************************	*****************		***************************************	
PBMC	CSR	_	ACD	8.5mL	_	34	l –	T -	17	68	_	34	68		I –	68	153	T	102	42.5	587
Serum ¹²	CSR		SST	8.5mL	_	25.5	8.5	8.5	8.5	25.5	_	_	17		_	_	25.5		17	17	153
Visit total					20	170	25	25	85	138	17	94	227		27	128	311		258	241	1762
56-Day total ¹⁰	f				20	190	215	240	324	462	478	332	475		27	154	465		258	241	1
URINE COLLECTION																					
Urine dipstick ⁶	Local lab	Local lab		,,,,,,,,,,,,,,,,,,,,,,,,,,,,,,,,,,,,,,,	X	_	—	T -	T -	Х	_	_			I –	T -	X		I –	I –	T
Pregnancy test ⁷	Local lab	Local lab			X	X		<del> </del>	T =	_	X				X	T _	 		X	 	1

¹ CSR = Central Specimen Repository; UW-VSL = University of Washington Virology Specialty Laboratory (Seattle, Washington, USA).

² HVTN Laboratories include: Fred Hutchinson Cancer Research Center (Seattle, Washington, USA); Duke University Medical Center (Durham, North Carolina, USA).

³ Local labs may assign appropriate alternative tube types for locally performed tests.

⁴ Screening may occur over the course of several contacts/visits up to and including day 0 prior to vaccination.

⁵ Chemistry panels are defined in Section 9.2 (pre-enrollment procedures) and Section 9.4 (follow-up visits).

⁶ And microscopy if needed.

⁷ For participants assigned female sex at birth. Pregnancy test may be performed on blood specimens. Persons who are NOT of reproductive potential due to having undergone total hysterectomy or bilateral oophorectomy (verified by medical records), are not required to undergo pregnancy testing

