⁸ At an early termination visit for a withdrawn or terminated participant who is not HIV-infected (see Section 9.12), blood should be drawn for HIV diagnostic testing, as shown for visit 16 above. If a participant has a confirmed diagnosis of HIV infection, do not collect blood for HIV diagnostic testing (see Section 9.14).

⁹ Fc-mediated Ab functions may include FcR binding assay, ADCC, ADNP ADCP, and complement assay.

¹⁰ The 56-day total blood volume does not include up to 16.5 mL blood collected for a reaction (see Section 9.10.1); however, the 56-day limit is not exceeded at any visit by this possible collection.

¹¹ Specimens indicated for Day 0 may be obtained within the 14 days prior to vaccination, except for a pregnancy test which must be performed on urine or blood specimens within 24 hours of vaccination with negative results received prior to vaccination.

¹² Antibody avidity, peptide microarray, metabolomic profiles, and proteomics assays may be done with serum collected for storage.

y = SST blood collected for the Binding Ab and Neutralizing Ab assays will also cover specimen needs for the Fc-mediated Ab function assays; no separate blood draw is needed.

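### Secondary endpoint 6 has no non-reactor comparator, so a change in reactors cannot be told apart from the ordinary innate response to vaccination

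*Protocol*

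**What the plan says.** Secondary objective 6 is worded the same way in Part B (Protocol 5.2.2) and Part C (5.3.2): "To characterize systemic inflammatory markers among participants with moderate to severe reactogenicity after any vaccination". Its endpoint covers flow-cytometry cell subsets, RNA transcripts and soluble mediators, "comparing day of last vaccination and day of visit for moderate to severe reactogenicity". No group without such reactions is named.

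The reaction-visit sample comes only from participants who react, and only at discretion (9.10.1): "Participants with evidence of moderate to severe reactogenicity may be asked to come to the clinic for additional assessment and/or blood sampling". The footnote to Appendix P gives its size: "The 56-day total blood volume does not include up to 16.5 mL blood collected for a reaction".

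Secondary endpoint 5 in the same sections measures leukocyte populations, RNA expression and serum cytokines and chemokines in all participants on Days 1, 3 and 7 against Day 0. Objective 5 is confined to the first vaccination. Section 10.3 likewise sets the primary innate timepoints at baseline and Days 1, 3 and 7 after dose 1. The background in 4.1.3 hopes that the study will "contribute a potential expanded safety marker panel".

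**The concern.** A before-after change in a reactor (here, a participant with moderate to severe reactogenicity) has two possible parts: the innate response that vaccination may produce in anyone, and whatever goes with the reaction itself. Endpoint 6 observes only the sum. An analyte that rises equally in everyone shows the same kind of change in reactors as one that truly tracks reactogenicity.

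What is at stake is how the result can be used. If endpoint 6 is to feed the safety marker panel mentioned in 4.1.3, non-specific analytes could be carried into later adjuvant studies. The objective also covers every vaccination, while the scheduled innate series that could serve as a reference follows dose 1 only.

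**Working it through.** The protocol gives no sample size, power or alpha for objective 6, so there is no figure of its own to reproduce. The check sets the endpoint against the sampling schedule and then illustrates the size of the problem.

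**1. The reaction draw matches the innate panel.** Appendix P volumes are 8.5 mL phenotyping, 3 mL RNA and 5 mL cytokines: 8.5 + 3 + 5 = 16.5 mL, the reaction-draw maximum. Endpoints 5 and 6 therefore appear to rest on the same three assays.

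**2. Which samples every participant gives.** Appendix P totals imply 51 / 8.5 = 6 phenotyping draws, 30 / 5 = 6 cytokine draws and 24 / 3 = 8 RNA draws. Placed by day since the preceding dose:

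| Time | Dose 1 | Dose 2 | Dose 3 |
|---|---|---|---|
| Pre-dose | all three (D0) | all three (D56) | all three (D168) |
| Days 1 and 3 | all three | none | none |
| Day 7 | all three | no innate tube, no serum; stored PBMC (D63, Visit 8) | no innate tube, no serum; stored PBMC (D175, Visit 12) |
| Day 14 | stored PBMC and serum | RNA; stored PBMC and serum (D70, Visit 9) | RNA; stored PBMC and serum (D182, Visit 13) |

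Footnote 9 of Appendices S and T places blood draws at vaccination visits before the injection, so D56 and D168 are baselines. The innate rows are the same in the other Part B tables (Appendices L to O).

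**3. What each contrast estimates.** Let V be the mean change due to vaccination in anyone and R the extra change that goes with a reaction.

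- Reactors against their own pre-dose sample: V + R.
- Reactors' change minus non-reactors' change on the same day: (V + R) − V = R.

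The first is endpoint 6 as written. The second can be formed after dose 1 from scheduled samples.

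**4. Illustration.** The assumptions are not from the protocol: change scores normal with SD 1, R = 0, 20 vaccinees of whom 4, 6 or 10 react, t-tests at two-sided 0.05, 20,000 runs. The middle columns give the share of runs in which the reactor-only test is significant although the marker has no link to reactogenicity.

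| Reactors / non-reactors | V = 0.5 SD | 1 SD | 1.5 SD | 2 SD | Against non-reactors |
|---|---|---|---|---|---|
| 4 / 16 | 11% | 29% | 54% | 76% | about 5% |
| 6 / 14 | 17% | 51% | 83% | 97% | about 5% |
| 10 / 10 | 30% | 80% | 99% | 100% | about 5% |

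**5. Whether another stated analysis fills the gap.** Section 6.4.4.1 plans repeated-measures analyses of innate trajectories, but over time and between treatment arms. Objective 5 compares regimens and correlates innate with adaptive responses. Neither sets reactors against non-reactors.

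**The case against.** The strongest reply is that the objective only sets out to characterize, within one subgroup, and a before-after comparison does that. The protocol nowhere says that a rise will be called a marker of reactogenicity, and the simulation tests a decision rule that the protocol does not state for endpoint 6. The panel in 4.1.3 is background for the whole study and does not mention this endpoint. All of this stands. A reader might infer that false marker claims are bound to follow; the text does not support that.

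A second reply is that the dose 1 reference samples already exist and that contrasting reactors with non-reactors is analysis detail for the SAP. The samples do exist. But the comparison is fixed in the endpoint wording, so it is a protocol choice. A SAP could add the dose 1 contrast; it could not add Day 1 to 3 draws after doses 2 and 3.

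Three further inferences are tempting and fail:

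- That only sustained reactions are sampled. The clause in 9.10, "is seen by a clinician within 48 hours after onset, unless the reaction is improving and/or has completely resolved", governs the clinician visit. Blood sampling falls under 9.10.1, which makes no exception for improving reactions.
- That adjuvant identity is mixed into the result. Section 6.4.4.1 summarises quantitative assay data by treatment arm.
- That no non-reactor reference at all exists after doses 2 and 3. PBMC are stored at Day 7, and 10.6.2 allows phenotyping on cryopreserved PBMC. RNA and stored serum exist at Day 14, which lies inside Part C's 14-day reactogenicity period, though outside Part B's 7 days. These are partial references.

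On proportion, this is the sixth secondary objective of a phase 1 trial with no decision attached. With 10 vaccinees per Part C arm, same-arm non-reactors may be few.

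**Conclusion.** The point holds in a limited form. As written, endpoint 6 estimates V + R and cannot isolate R, so it cannot by itself support a reactogenicity-specific conclusion or a contribution to the safety marker panel. This follows from the endpoint wording and the sampling schedule and needs no numerical assumption. The illustrative rates (11% to 100% against about 5%) do depend on the assumed SD, rise and number of reactors, and show only the possible scale.

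After dose 1 the gap can be closed with scheduled samples. After doses 2 and 3 it is firm for all three assays on Days 1 to 3 and for serum through Day 7, and partial beyond that.

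**What to change.** Amend secondary endpoint 6 in 5.2.2 and 5.3.2 as follows:

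- After dose 1, compare reactors' change from pre-dose with that of participants without moderate to severe reactions, at the nearest scheduled day (1, 3 or 7). Do this within arm, or adjusted for arm where arms are small.
- Base any reactogenicity-specific conclusion on that comparison.
- Report reaction-visit samples after doses 2 and 3 descriptively, showing the day since vaccination.

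The cost is endpoint wording and a little more analysis, with no new draws. Part B enrollment is already complete (Section 4.5), so wording and analysis are the practical lever there. The downsides are few participants per arm in Part C and specific conclusions limited to dose 1.

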5.3.3 Exploratory objectives for Part C

Exploratory objective 1:

To further evaluate immunogenicity of each vaccine regimen, additional immunogenicity assays may be performed in a subset of participants, including on samples from other timepoints, based on the HVTN Laboratory Assay Algorithm

Exploratory objective 2:

To conduct analyses related to furthering the understanding of HIV, immunology, vaccines, adjuvant effects, and clinical trial conduct

6 Statistical considerations

